Re-randomization (subjects entering Double-blind Maintenance Phase only)						✓	

Abbreviations: DUCS=Daily Ulcerative Colitis Scale for children and caregivers; eCRF=electronic case report form; e-diary=electronic diary; IRT= interactive response technology; PGA=Physician's Global Assessment; PUCAI=Pediatric Ulcerative Colitis Activity Index; UC-DAI=Ulcerative Colitis Disease Activity Index.

^a Approximately 4 to 7 days prior to the Baseline Visit (Visit 2) and prior to each subsequent visit (Visits 3, 3.1, and 3.2), it is recommended that site staff telephone the subject or the subject's caregiver to remind them to enter UC-DAI symptoms (rectal bleeding and stool frequency) into the e-diary every night, even if the subject has no symptoms.

^b Subjects may enter into the Open-label Acute Phase beginning at Visit 3 (after a minimum of 2 weeks double-blind treatment) and at any time until the end of the Double-blind Acute Phase provided all criteria have been met.

^c Subjects will continue into the Open-label Acute Phase if they have not met the criteria to enter the Double-blind Maintenance Phase and are eligible to continue into the Open-label Acute Phase.

^d Subjects will continue into the Double-blind Maintenance Phase if partial UC-DAI ≤ 1 (with rectal bleeding=0 *and* stool frequency ≤ 1 *and* PGA=0) *and* with mucosal healing (endoscopy score)=0 or 1, and are eligible to continue into the Double-blind Maintenance Phase.

^e This will be the final visit for subjects not entering the Open-label Acute Phase or the Double-blind Maintenance Phase.

^f The Baseline Visit (Visit 2) does not need to be repeated for subjects entering the Double-blind Maintenance Phase at the end of the Double-blind Acute Phase. Visit 3.2 will be considered the Week 0 visit for the next phase into which subjects are continuing.

^g Follow-up assessment in this phase applies only to subjects who are discontinuing the study; may be performed via telephone call within 7 days of the last dose of investigational product.

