7.1.3 Open-label Acute Phase

Subjects may enter the Open-label Acute Phase after completion of the Double-blind Acute Phase if they do not meet the requirements for entry into the Double-blind Maintenance Phase ie, they do not achieve a clinical response defined as a partial UC-DAI ≤ 1 (with rectal bleeding=0 *and* stool frequency ≤ 1 *and* PGA=0). This phase is intended to allow those subjects without clinical response in the Double-blind Acute Phase an additional 8 weeks to achieve clinical response at the high dose for their weight group. The subject's weight at Visit 3.2 (Week 8/Withdrawal of the Double-blind Acute Phase) will be used to determine the high dose assigned to the subject in the Open-label Acute Phase.

Subjects are also eligible for the Open-label Acute Phase provided they have participated in the Double-blind Acute Phase for a minimum of 2 weeks and, in the investigator's opinion, have not benefited from treatment in the Double-blind Acute Phase. In addition, they should not have experienced a possibly or probably related severe adverse event (AE) or a serious AE (SAE). Due to the delay in onset of action of 5-ASA preparations, investigators should make subjects/caregivers aware that they may not benefit from the investigational product within the first 2 weeks. Subjects who withdraw before Visit 3 will not be eligible for the Open-label Acute Phase.

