3. STUDY DESIGN

3.1 General Description

This study will be conducted in children and adolescents (aged 5-17 years) to collect data on the safety and efficacy of MMX mesalamine/mesalazine in this population. This study is a PREA post-approval commitment with the US FDA and is intended to provide estimates of clinical response for 2 doses (low and high) across a range of weight groups.

This study will enroll male and female children and adolescents aged 5-17 years. This is a prospective, parallel-group study with an 8-week Double-blind Acute Phase, and a 26-week Double-blind Maintenance Phase. More than 100 subjects will be screened, and up to 80 subjects will be enrolled in the Double-blind Acute Phase of the study. After agreement with FDA, the sample size for the Double-blind Acute Phase has been reduced to 53 subjects due to difficulties with recruitment.

More than 65 subjects will be screened (in addition to an expected 28 subjects who will enter the Double-blind Maintenance Phase from one of the Acute Phases) and at least 80 subjects will be enrolled in the Double-blind Maintenance Phase of the study.

Each phase includes 2 treatment arms, and subjects will be randomized at the beginning of each phase to 1 of 2 doses (low and high dose) of MMX mesalamine/mesalazine (900-4800mg/day, given once daily), stratified by weight group. There is an additional 8-week, Open-label Acute Phase for subjects who do not achieve a clinical response or who have withdrawn from the Double-blind Acute Phase and have met certain criteria (see [Figure 1](#)). Clinical response is defined as partial Ulcerative Colitis Disease Activity Index (UC-DAI) ≤ 1 (with rectal bleeding=0 and stool frequency ≤ 1 and Physician's Global Assessment [PGA] =0) at the end of the Double-blind Acute Phase. In this Open-label Acute Phase, subjects are treated with the high dose of MMX mesalamine/mesalazine for their weight group.

Subjects with a clinical response after completion of treatment in either the Double-blind Acute Phase or the Open-label Acute Phase will be eligible to enter the Double-blind Maintenance Phase based on partial UC-DAI score (i.e., without additional endoscopy).

Subjects without a clinical response after completion of acute treatment in the Open-label Acute Phase must be withdrawn.

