5.6.1 Exposure to Investigational Product

Exposure to investigational product will be summarized separately for each of the three Safety Analysis Sets (Double-blind Acute Phase, Open-label Acute Phase and Double-blind Maintenance Phase). Summary statistics (n, mean, SD, median, Q1, Q3, minimum, and maximum) for the duration of treatment exposure will also be presented.

Exposure will be summarized in terms of total dose, average daily dose, and length of exposure for each phase, calculated for each subject as:

- Total Dose (mg) = sum of doses within phase of interest
- Average Daily Dose (mg/day) = Total Dose / total days of dosing within phase of interest
- Length of Exposure (weeks) = (Date of last dose within phase of interest – date of first dose within phase of interest + 1) / 7

Additionally, to examine subject-level exposure across study phases, these parameters will be listed by subject and phase.

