5.9.1 Adverse Events

Adverse events will be coded using Version 16.1 (or newer) of Medical Dictionary for Regulatory Activities (MedDRA). The number and percentage of subjects with an event, as well as the number of events will be reported for each summary.

An AE (classified by preferred term) that occurs during the study will be considered a treatment-emergent AE (TEAE) if it has a start date on or after the first dose of investigational product or if it has a start date before the date of the first dose of investigational product, but increases in severity on or after the date of the first dose of investigational product. If more than 1 AE with the same preferred term is reported before the date of the first dose of investigational product, then the AE with the greatest severity will be used as the benchmark for comparison to the AEs occurring during the study under the preferred term. An AE that occurs more than 7 days after the date of the last dose of investigational product of that phase will not be counted as a TEAE.

An overall summary of the number of subjects with TEAEs and number of TEAEs will be presented overall for the Overall Safety Analysis Set, an overall summary of the number of subjects with TEAEs and number of TEAEs will be presented for High-dose MMX only for Open Label Acute Phase Safety Analysis Set, and by treatment group and overall for the Double-blind Acute and Double-blind Maintenance Phase Safety Analysis Sets. The summary will include the number and percentage of subjects with any TEAEs, serious TEAEs, TEAEs related to investigational product, TEAEs leading to discontinuation of investigational product and TEAEs leading to death.

The number and percentage of subjects reporting TEAEs, as well as the number of events, will be tabulated by system organ class (SOC) and preferred term for Overall Safety Analysis set, the Double-blind Acute and Double-blind Maintenance Phase Safety Analysis Sets, and also for Open-label Acute Phase Safety Analysis Set.

The number and percentage of subjects reporting TEAEs will also be tabulated by SOC, preferred term, and maximum severity for Overall Safety Analysis set, Double-blind Acute and Double-blind Maintenance Phase Safety Analysis Sets, and also for Open-label Acute Phase Safety Analysis Set.

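### Adverse events are compared by arm only as crude percentages and counts, although blinded follow-up can end early for lack of benefit; if exits differ by arm, the comparison can mislead in either direction

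*SAP*

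**What the plan says.** SAP 5.9.1 sets the summary measure for adverse events: "The number and percentage of subjects with an event, as well as the number of events will be reported for each summary". The overview of treatment-emergent adverse events (TEAEs) is given "and by treatment group and overall for the Double-blind Acute and Double-blind Maintenance Phase Safety Analysis Sets". Protocol 9.9 plans the same kind of summary. Neither document, nor the SAP list of tables in Section 10, contains a rate per person-time or a time-to-first-event analysis.

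The planned follow-up is "an 8-week Double-blind Acute Phase, and a 26-week Double-blind Maintenance Phase" (SAP 3.1), but it can be shorter:

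- **Acute phase.** Protocol Table 1, footnote b: "Subjects may enter into the Open-label Acute Phase beginning at Visit 3 (after a minimum of 2 weeks double-blind treatment". Protocol 7.1.3 allows this for children who, in the investigator's opinion, "have not benefited from treatment in the Double-blind Acute Phase".
- **Maintenance phase.** Protocol 4.5.1 lists lack of efficacy among the reasons for discontinuation. Protocol 5.3 requires withdrawal when certain other colitis treatments are used.
- **Event window.** "An AE that occurs more than 7 days after the date of the last dose of investigational product of that phase" is not counted as a TEAE (SAP 5.9.1). The section does not say that this window closes when the next phase's drug is started.

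SAP 5.6.1 states: "Exposure will be summarized in terms of total dose, average daily dose, and length of exposure for each phase". SAP 5.6 presents this by arm for the blinded phases, and SAP 5.3 gives discontinuations and their primary reasons by arm.

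**The concern.** A crude percentage compares arms fairly only if children in both arms are observed for similar lengths of time. Here observation can end for a reason tied to the primary question, namely whether the dose is working. If one dose works less well, more of its children can be expected to leave early, and their later adverse events fall outside that phase's tables.

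Safety and tolerability of the two doses is a stated objective (SAP 2.2.3), and the data are meant to help choose paediatric doses (SAP 1.2). A difference in TEAE percentages produced partly by unequal follow-up could be read as a difference in tolerability. The SAP already derives length of exposure per phase but does not bring it into any adverse event output.

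**Working it through.** The documents give no adverse event rate, exit rate or expected exposure, so there is no planned figure to reproduce. What follows is an illustration.

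**Inputs from the documents:** phases of 8 and 26 weeks; earliest switch at Week 2; TEAE window to 7 days after last dose; 53 children in the acute phase (SAP 3.5), allocated 1:1, so about 26 and 27 per arm; at least 80 in maintenance, so about 40 per arm.

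**Assumed inputs:** the same constant hazard in both arms; eight-week incidence R; a fraction f leaving at week t (2 or 4), with everyone else staying 8 weeks.

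**Formulas**

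- Hazard: h = −ln(1 − R)/8
- Crude percentage: f(1 − e^(−ht)) + (1 − f)R
- Mean exposure: f·t + 8(1 − f)
- Artefact between arms: (f₁ − f₂) × [e^(−ht) − (1 − R)]

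**Main range, 30% versus 10% leaving**

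- R = 30%, t = 4: 0.20 × (0.8367 − 0.70) = 2.7 points.
- R = 50%, t = 2: 0.20 × (0.8409 − 0.50) = 6.8 points.
- Mean exposure: 6.2 to 6.8 weeks versus 7.4 to 7.6 weeks.
- With the 7-day tail (5 or 3 weeks versus 9): 0.20 × (0.8002 − 0.6695) = 2.6 and 0.20 × (0.7711 − 0.4585) = 6.3 points.

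**Other scenarios, no tail**

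| R | Leaving | Week | Gap (points) |
|---|---|---|---|
| 20% | 20% v 10% | 4 | 0.9 |
| 40% | 20% v 10% | 4 | 1.7 |
| 40% | 30% v 10% | 4 | 3.5 (34.8% v 38.3%) |
| 40% | 30% v 10% | 2 | 5.6 |
| 40% | 50% v 10% | 2 | 11.2 |
| 60% | 50% v 10% | 2 | 15.8 |
| any | equal | any | 0 |

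In each row the first-event rate per subject-week is the same in both arms by construction (6.39 per 100 subject-weeks at R = 40%).

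**Maintenance.** Assuming 50% incidence over 26 weeks and 30% versus 10% leaving at Week 13: 0.20 × (0.7071 − 0.50) = 4.1 points.

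**Direction.** Protocol 8.1.4 makes significant symptom worsening a recordable adverse event. Take R = 40%, 30% versus 10% leaving at Week 4, and let a share w of leavers also have such an event. Their risk becomes 1 − 0.7746(1 − w).

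| w | Gap (points) |
|---|---|
| 0 | 3.5 |
| 10% | 1.9 |
| 25% | −0.4 |
| 50% | −4.3 |

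The gap is zero at w = 1 − 0.60/0.7746, or about 22.5%. Above that, the arm with more exits looks less safe.

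**Sampling error.** The 95% half-width for a difference with 26 v 27 children is 1.96 × √[p(1 − p)(1/26 + 1/27)], which is 21.5 points at p = 20% and 26.4 points at 40% or 60%. With 40 per arm and p = 50% it is 1.96 × √(0.25 × 2/40) = 21.9 points.

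**The case against.** The case for leaving the SAP alone has several parts.

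- **An imbalance would be seen.** Exposure is tabulated by arm (SAP 5.6; tables 14.3.8.4 and 14.3.8.6), as are discontinuations and reasons, and event counts accompany the percentages. A reader could form a rough rate for all events. This stands, but visible is not the same as adjusted for: a first-event rate cannot be built from those tables, because time to first event is not tabulated.
- **The artefact is within the noise.** Every scenario above is smaller than the sampling half-width, no test of adverse events between arms is planned, and SAP 5.1 treats p-values as descriptive. This stands and limits the importance of the point. It does not remove it, because in an estimation study the estimate itself should be interpretable.
- **Exit at Week 2 may be uncommon.** Protocol 7.1.3 asks investigators to tell families that benefit may not appear within the first two weeks. That weighs against the largest figures, which need many exits at Week 2.
- **Rates have weaknesses too.** If leavers tend to have worsening recorded, their shorter person-time inflates the rate in that arm. At about 26 per arm, rates by system organ class or preferred term would rest on one or two events. Both points stand and shape the fix.

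A reader might also infer that the less effective dose is bound to have less exposure and to look safer. The documents do not support that. They give no exit rates; equal exit produces no artefact; events that all start in the first two weeks would produce almost none; and Protocol 8.1.4 can turn the sign round.

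**Conclusion.** The point holds in conditional form. The planned measures take no account of time at risk, while the design allows that time to be cut short for lack of benefit. If the doses differ in efficacy, the crude percentages can mislead: towards the arm with more exits for events that accrue over time, or against it if colitis worsening is often recorded in those who leave. Under the assumed exits of 30% versus 10% the size is about 2.7 to 6.8 points, or 2.6 to 6.3 with the 7-day tail. It rests wholly on assumed exit and event rates and on a constant, equal hazard.

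There is also a gap in attribution. As written, an event in a child's first week on open-label high dose could count under the blinded arm as well as the open-label phase.

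This is a cheap improvement to the safety reporting, not a flaw that invalidates the planned tables.

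**What to change.** Keep the existing tables. Add to SAP 5.9.1, by arm for both blinded phases and only for the overall TEAE lines (any, serious, related):

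1. Children with a first event per 100 subject-weeks at risk, with the rate difference and its 95% CI.
2. Cumulative incidence of first TEAE to Week 8 (acute) or Week 26 (maintenance), which does not need a constant hazard.

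State that time at risk and event attribution for a blinded phase end at the first dose of the next phase, including open-label, and otherwise 7 days after last dose. Show colitis-worsening events on their own line, using a list of terms fixed before unblinding, so that lack of efficacy is not mixed with drug toxicity. Leave the system organ class and preferred term tables as percentages and counts.

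Cost: a small amount of programming from event and dosing dates that are already collected. The rate in item 1 assumes a roughly constant hazard. Both items treat leaving as uninformative about later events, so they should be read beside the discontinuation tables.

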8.1.1 Severity Categorization

The severity of AEs must be recorded during the course of the event including the start and stop dates for each change in severity. An event that changes in severity should be captured as a new event. Worsening of pre-treatment events, after initiation of investigational product, must be recorded as new AEs (for example, if a subject experiences mild intermittent dyspepsia prior to dosing of investigational product, but the dyspepsia becomes severe and more frequent after first dose of investigational product has been administered, a new AE of severe dyspepsia [with the appropriate date of onset] is recorded in the appropriate eCRF).

The medical assessment of severity is determined by using the following definitions:

Mild: A type of AE that is usually transient and may require only minimal treatment or therapeutic intervention. The event does not generally interfere with usual activities of daily living.

Moderate: A type of AE that is usually alleviated with specific therapeutic intervention. The event interferes with usual activities of daily living, causing discomfort but poses no significant or permanent risk of harm to the research subject.

Severe: A type of AE that interrupts usual activities of daily living, or significantly affects clinical status, or may require intensive therapeutic intervention.

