8.2.5 Serious Adverse Event Onset and Resolution Dates

The onset date of the SAE is defined as the date the event meets serious criteria. The resolution date is the date the event no longer meets serious criteria, the date the symptoms resolve, or the event is considered chronic. In the case of hospitalizations, the hospital admission and discharge dates are considered the onset and resolution dates, respectively.

In addition, any signs or symptoms experienced by the subject after signing the informed consent form, or leading up to the onset date of the SAE, or following the resolution date of the SAE, must be recorded as an AE, if appropriate.

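### SAP 5.9.1 counts each severity step of one adverse event as a separate TEAE, so the reported number of events is inflated even when events ease

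*SAP*

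**What the plan says.** Three rules interact.

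- **Recording.** Protocol 8.1.1 asks sites to record severity "including the start and stop dates for each change in severity" and then states: "An event that changes in severity should be captured as a new event". No direction is given. A separate sentence covers deterioration of earlier events: "Worsening of pre-treatment events, after initiation of investigational product, must be recorded as new AEs".
- **Classification.** Under SAP 5.9.1 an AE "will be considered a treatment-emergent AE (TEAE) if it has a start date on or after the first dose of investigational product". The alternative limb, joined by an or, covers an AE that starts before that date "but increases in severity on or after the date of the first dose of investigational product". Events occurring more than 7 days after the last dose of the phase are not counted. Where a subject has more than one pre-dose AE of the same preferred term, "the AE with the greatest severity will be used as the benchmark for comparison to the AEs occurring during the study under the preferred term".
- **Counting.** SAP 5.9.1 opens its reporting rules with: "The number and percentage of subjects with an event, as well as the number of events will be reported for each summary". Its one rule on repeated preferred terms counts the subject once, at the worst severity and closest relationship, for the severity and relationship summaries. It says nothing about how many events to count.

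SAP Section 8 deals with missing AE dates, severity and causality. Neither that section nor 5.9.1 links consecutive records of one continuing event.

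**The concern.** Each rule is reasonable alone. Together they make the event count depend partly on how many severity levels an episode passes through. A headache that resolves stepwise yields more events than one that stays at the same intensity throughout, so improvement raises the count.

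Safety and tolerability of the low and high dose is a stated objective in all three treatment phases, and Protocol 9.9 also calls for the number of TEAEs by treatment group. A reader comparing the two doses would take these figures as numbers of distinct events. The programmer, meanwhile, must either count records or invent a joining rule that the SAP does not contain.

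**Working it through.** The plan states no figure to reproduce. The check applies the recording rule and the TEAE rule to five example courses of one event.

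**Inputs.** Every severity change gives a new record with its own start date (Protocol 8.1.1). The first TEAE limb carries no severity condition, and the window closes 7 days after the phase's last dose (SAP 5.9.1).

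**Two readings.**
- *Literal:* every record starting inside the window is a TEAE.
- *Benchmark:* a record inside the window is a TEAE only if it is more severe than the worst pre-dose record of the same preferred term. This extends the benchmark sentence to the case of a single pre-dose AE.

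**Formulas.** For an episode that begins on treatment, events counted = 1 + number of severity changes inside the window, under either reading, because there is no pre-dose record to compare with. For an episode that begins before dosing, the literal count is the number of severity changes inside the window.

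| Course of one event | Literal | Benchmark | One count per episode |
|---|---|---|---|
| A. Begins on treatment: severe, moderate, mild | 1 + 2 = 3 | 3 | 1 |
| B. Begins on treatment: moderate, mild | 1 + 1 = 2 | 2 | 1 |
| C. Pre-dose moderate, eases to mild after first dose | 1 | 0 | 0 |
| D. Pre-dose mild, worsens to severe, eases to mild | 2 | 1 | 1 |
| E. Begins on treatment: mild, no change | 1 + 0 = 1 | 1 | 1 |

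Rows A and B give the same excess under both readings, so the core finding does not depend on interpretation. Rows C and D do depend on it. In C the subject also becomes a TEAE subject on the literal reading and not on the other.

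**Over a whole phase.** For N episodes that begin on treatment, with an average of m severity changes each inside the window, the reported number of events is N × (1 + m). Neither document gives m.

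**Across phases.** Take an event that begins in an acute phase and eases during Maintenance dosing. The easing step is a record that starts after first dose and inside the Maintenance window, so the 7-day limit does not remove it. On the literal reading it is one Maintenance TEAE under the newly assigned dose. Protocol 9.6 expects 28 subjects to enter Maintenance from the acute phases, which is the group in which this can happen.

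**The case against.** **Most tables are safe.** A subject with several records of one term is counted once in any number-and-percentage column, and SAP 5.9.1 says so explicitly for severity and relationship. A reader might infer that the percentage of children with a TEAE is overstated generally. For events that begin on treatment it is not, and the maximum-severity tables are also unaffected. What remains is the number of events. It is descriptive, no test or exposure-adjusted rate is planned on it, and the same recording rule applies to both blinded arms. This limits the consequences; it does not make the count correct.

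**The literal reading of pre-dose events leaves other text idle.** Protocol 8.1.1 already gives every worsening a new post-dose record, so on the literal reading the second TEAE limb would almost never operate and the benchmark would do nothing. A reader might therefore want to say that easing pre-dose events certainly inflate incidence. The documents do not support that: the benchmark sentence points to an intended comparison with pre-dose severity. But it is written only for more than one pre-dose AE, and it does not say that it overrides the first limb. The case is ambiguous.

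**Phase attribution.** SAP 5.9 lists AEs among the safety variables and sets baseline or Week 0 as the last value before first dose in the phase of interest. That gives some support for judging a Maintenance event against its status at entry, so misattribution to the new dose is possible rather than established.

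**Other sources of extra records.** A reader might add the signs or symptoms that, "following the resolution date of the SAE, must be recorded as an AE, if appropriate" (Protocol 8.2.5). That instruction is conditional, and such symptoms may carry other preferred terms. Nor can ordinary fluctuation of colitis symptoms be added: Protocol 8.1.4 keeps it out of the AE data unless there is significant worsening.

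**Unseen specifications.** SAP 1.1 places table specifications in a separate document, which might hold a counting rule. The SAP does not refer to one.

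**Conclusion.** The concern holds for the number of TEAEs. Followed as they stand, the two documents add one event for each severity step of an episode that begins on treatment: two events for moderate to mild, three for severe to moderate to mild. This rests on sites recording as Protocol 8.1.1 instructs and on no joining rule existing outside the SAP.

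The overall size cannot be estimated. Any percentage inflation would rest on an assumed rate of severity change for which the documents give no basis. The comparison between doses is distorted only to the extent that severity steps per episode differ between arms.

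For events that began before dosing or in an earlier phase and then only ease, the finding is narrower: the text permits them to be counted as new TEAEs, probably against its intent, and should be made to exclude them.

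**What to change.** Amend SAP 5.9.1 as follows.

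1. For event counts, join consecutive records of the same preferred term that differ only in severity and are contiguous in date (one stops on the day the next starts, or the day before) into one episode. Count it once, at maximum severity, in the phase where it began.
2. State that a record continuing a pre-dose or prior-phase event is a TEAE of the later period only if its severity exceeds the worst severity of that preferred term before that period's first dose, including when there was only one earlier AE.
3. Where a stop date is partial, treat the records as contiguous if the known date parts allow it. This line is needed because SAP 8.7 and 8.7.2 impute only AE start dates.
4. Keep every record in the listings.

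The cost is SAP wording and one derivation, including the partial-date rule, on data already collected. Reported event counts will fall where episodes were split. Subject-level results for events that begin on treatment will not change.
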